Baseline blood samples (12 mL), saliva (1-2 mL) and urine will be collected and analyzed for buprenorphine and metabolites. We will perform a urine drug screen by immunoassay for drugs of abuse. Blood will also be utilized for determination of catecholamines (epinephrine and nor epinephrine), cotinine, and PBMC analysis. Screening blood chemistries and hematology labs

(AST/SGOT, ALT/SGPT, creatinine, BUN, total protein, albumin, hemoglobin, and platelets) are collected at the first Screening Visit only to establish eligibility. A hematocrit is also required at the first screening visit, unless a result is available from the subject's medical record within the past 4 weeks. If the hematocrit is within normal limits at the first screening visit, it will not be repeated during the remainder of the study. Baseline physiologic measurements (pupillometry, galvanic skin response, blood pressure, and heart rate) will be taken and the subject will subsequently take her medication as prescribed.

Additional blood and saliva samples will be collected at the following time intervals. The maximum amount of blood drawn from a subject on a study day is 103 mL.

Sample/Measurement Type	Dosing	Time Interval
blood & saliva	BID	Baseline and 10, 20, 30, 60, 90, 120, 180, 240, 360, 480, 600, 720 minutes post dose
blood & saliva	TID	Baseline and 10, 20, 30, 60, 90, 120, 180, 240, 300, 360, 420, 480 minutes post dose
blood & saliva	QID	Baseline and 10, 20, 30, 60, 90, 120, 180, 240, 300, 360 minutes post dose
blood & saliva	5 times/day	Baseline and 10, 20, 30, 60, 90, 120, 150, 180, 240, and 300 minutes post dose

Refer to section D.5.xi for blood and saliva collection and processing instructions.

All urine voided from 0-12 hrs. (subject will be asked to empty bladder at 12 hrs for BID dosing, at 8 hours for TID dosing, at 6 hours for QID dosing, and at 5 hours for five times daily dosing) will be collected, total volume recorded and aliquots will be frozen immediately.

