The following collection and processing instructions apply to all blood and saliva samples collected during this study. The samples collected will be dependent on which parts of the study the subject participates in.

Blood samples will be collected as follows:

- Maternal and Cord Blood Samples for BUP Analysis: One 10 mL heparinized vacutainer tube will be drawn at the time points described in sections D.5.vi and D.5.ix. The tube should be centrifuged at 1500 g at 4°C for 15 minutes. Plasma samples will then be transferred into polypropylene tubes and frozen at -80 degrees centigrade until analysis.
- PBMC analysis: One 5 mL EDTA vacutainer tube will be drawn with the first sample (pre-dose) at each PK study visit and at delivery (applicable to all subjects), when possible. The sample should be stored at room temperature. Notify [name] lab in advance at [contact] / [contact] or via email ([contact]) to allow for pick up and processing within 4 hours of collection.
- DNA Analysis: One 10 mL EDTA vacutainer tube will be drawn at the Baseline Screening Visit. If the DNA sample is unable to be obtained at the screening visit, it may be collected anytime during the study when blood is being drawn. The sample should be frozen at -80 degrees centigrade until analysis.

Saliva samples will be collected using a Sarstedt Salivette collection device. The salivary collection sponge can be centrifuged later in the day. Salivary pH will be determined. Oral fluid samples will then be transferred into polypropylene tubes and frozen at -80 degrees centigrade until analysis.

D.5.xii. Study Outcome Measures and Ascertainment (Applicable to all Subjects):

Mothers and infants will be followed until they are discharged from the hospital, at which time relevant data from the labor, delivery and nursery records will be recorded.

a. Primary Outcome:

The primary outcome is the exposure to BUP (AUC) during pregnancy and the post-partum state.

b. Secondary Outcomes Maternal:

Other maternal outcomes to be measured are:

1. The relationship between COW and Craving scores, pupillometry, heart rate, blood pressure

and GSR scores to the maternal plasma concentration of BUP and its major metabolites

2. The impact of polymorphisms of CYP 450 and conjugating enzymes of buprenorphine on plasma concentration of BUP and its major metabolites
3. The relationship between the umbilical cord and maternal concentration of BUP and its major metabolites

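### The 103 mL daily blood maximum and 12 mL baseline in D.5.vi do not match the tube instructions in D.5.xi, which sum to 110–135 mL at nominal fill

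*Combined protocol and SAP*

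**What the plan says.** D.5.vi (blood, urine, saliva and breast milk collection) gives two volumes for a PK study day. The ceiling is "The maximum amount of blood drawn from a subject on a study day is 103 mL". The pre-dose volume is "Baseline blood samples (12 mL), saliva (1-2 mL) and urine will be collected and analyzed". The same paragraph adds catecholamines, cotinine and PBMC analysis to the uses of the blood, without a tube or volume for any of them.

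D.5.vi then lists the sampling times. For BID dosing they are "Baseline and 10, 20, 30, 60, 90, 120, 180, 240, 360, 480, 600, 720 minutes post dose", and for QID dosing "Baseline and 10, 20, 30, 60, 90, 120, 180, 240, 300, 360 minutes post dose". TID has as many times as BID, and five-times-daily has as many as QID. The table in D.1 gives the same counts: baseline plus 12, or baseline plus 10.

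For how to collect the samples, D.5.vi says: "Refer to section D.5.xi for blood and saliva collection and processing instructions". D.5.xi then specifies, for buprenorphine: "One 10 mL heparinized vacutainer tube will be drawn at the time points described in sections D.5.vi and D.5.ix". For PBMC it says: "One 5 mL EDTA vacutainer tube will be drawn with the first sample (pre-dose) at each PK study visit". The PBMC instruction is qualified: "at each PK study visit and at delivery (applicable to all subjects), when possible". D.5.xi also has a 10 mL DNA tube, normally taken at screening but allowed at any later blood draw. Neither section states how much blood goes into each tube.

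**The concern.** The ceiling and the collection instructions are in the same document and one refers to the other, so the tubes should add up to no more than the ceiling. On an ordinary reading they do not, under any of the four dosing schedules.

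The figure limits blood taken from pregnant and postpartum women who may have up to three PK days. The protocol treats blood burden as relevant: a hematocrit below 28 excludes a woman from the PK study (D.4.ii), and D.5.v gives fewer blood samples as one reason for restricting the dosing schedules. A normal first hematocrit is not repeated (D.5.vi). The study is multicenter and each center writes its own consent form (D.4.iv), so sites need one reliable volume. As written, staff who fill the tubes exceed the stated maximum, and staff who keep to the maximum must choose a draw volume themselves.

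**Working it through.** **Inputs**

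- Stated daily maximum 103 mL and stated baseline 12 mL (D.5.vi).
- Draws per PK day (D.5.vi, confirmed by D.1): BID and TID 1 + 12 = 13; QID and five times daily 1 + 10 = 11.
- Buprenorphine tube 10 mL per time point; PBMC tube 5 mL pre-dose, when possible; DNA tube 10 mL if deferred to a PK day (D.5.xi).
- Assumption: each tube is filled to nominal volume. The documents do not say this.

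**Step 1. Can 103 mL be reproduced?** The daily total is draws × 10 mL, plus any other tubes.

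| Sum | BID / TID | QID / five times daily |
|---|---|---|
| Buprenorphine tubes only | 13 × 10 = 130 mL | 11 × 10 = 110 mL |
| Plus PBMC tube | 130 + 5 = 135 mL | 110 + 5 = 115 mL |
| Plus PBMC and deferred DNA tube | 135 + 10 = 145 mL | 115 + 10 = 125 mL |
| Stated 12 mL baseline, 10 mL per post-dose draw | 12 + 12 × 10 = 132 mL | 12 + 10 × 10 = 112 mL |

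No combination gives 103 mL, and the smallest is 110 mL.

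**Step 2. Size of the excess over 103 mL**

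- Buprenorphine tubes only: 130/103 = 1.262 (+26%, 27 mL); 110/103 = 1.068 (+7%, 7 mL).
- With the PBMC tube: 135/103 = 1.311 (+31%, 32 mL); 115/103 = 1.117 (+12%, 12 mL).

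**Step 3. Baseline.** The buprenorphine tube alone is 10 mL. With the PBMC tube it is 10 + 5 = 15 mL, and 15/12 = 1.25 (+25%). The stated 12 mL equals neither.

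**Step 4. Draw volume that would fit.** These are the largest average volumes that keep the day within 103 mL.

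| Basis | BID / TID | QID / five times daily |
|---|---|---|
| No PBMC tube, per draw | 103/13 = 7.92 mL | 103/11 = 9.36 mL |
| PBMC tube counted, per buprenorphine draw | (103 − 5)/13 = 7.54 mL | (103 − 5)/11 = 8.91 mL |
| 12 mL baseline kept, per post-dose draw | (103 − 12)/12 = 7.58 mL | (103 − 12)/10 = 9.10 mL |

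All are below 10 mL, so every schedule needs part-filled or smaller tubes to stay within the maximum.

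**Step 5. A possible origin for the figures.** With 7 mL per buprenorphine draw, the baseline would be 7 + 5 = 12 mL. A BID or TID day would be 12 + 12 × 7 = 96 mL and a QID or five-times-daily day 12 + 10 × 7 = 82 mL. Also, 12 + 13 × 7 = 103 mL, but that needs 13 post-dose draws, one more than any schedule lists. A 7 mL draw appears nowhere in the documents.

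**The case against.** The strongest reply is that a tube size is not a draw volume. D.5.xi names a 10 mL tube and does not require 10 mL of blood, while D.5.vi sets a maximum. Both can hold if the tubes are part-filled. The 7 mL pattern in Step 5 supports this reading: it gives the stated 12 mL baseline exactly and keeps every schedule below 103 mL. A maximum need only be at or above the total, so it is no objection that the sum is 96 mL rather than 103 mL.

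This stands in part. Every percentage above depends on nominal fill, and the sums do not prove that a woman has more than 103 mL drawn. But the 7 mL volume is an inference. D.5.vi sends the reader to D.5.xi, and D.5.xi gives only the tube.

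The baseline comparison is weaker. The 12 mL is attached to samples for buprenorphine and metabolites, and PBMC is mentioned later, so it is unclear whether the 12 mL includes the PBMC tube. If it does not, a single 10 mL tube is nominally too small for 12 mL. If it does, the tubes sum to 15 mL. The mismatch remains on either reading, but its size is uncertain.

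A manual of operations, cited in D.4.iii for gestational age, and the site consent forms were not available. Either might give a per-draw volume. That limits the conclusion to this document. The PBMC tube being collected only when possible does not help, because the buprenorphine tubes alone exceed the maximum.

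**Conclusion.** The point holds, and D.5.vi and D.5.xi are inconsistent as written. At nominal fill, the specified tubes exceed the stated 103 mL by 7–12 mL (7–12%) for QID and five-times-daily dosing and by 27–32 mL (26–31%) for BID and TID dosing. In each range the lower figure omits the PBMC tube and the upper includes it. The stated 12 mL baseline matches neither 10 mL nor 15 mL. A DNA tube deferred to a PK day would raise the totals to 125 mL or 145 mL.

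The draw counts and tube sizes come directly from the protocol; the only assumption is that tubes are filled to nominal volume. The documents do not show which figure is right, or that more than 103 mL is actually drawn. This should be corrected because it concerns a stated limit on blood volume in pregnant and postpartum women. It has no bearing on sample size, power or the AUC comparison.

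**What to change.** Reconcile D.5.vi with D.5.xi in one of two ways:

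- state in D.5.xi a volume per draw, or a tube size, whose sum over 13 or 11 draws plus all baseline tubes is within the stated maximum; or
- restate the daily maximum and the baseline volume in D.5.vi as the true sums for each dosing regimen.

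In either case, list what makes up the baseline volume (buprenorphine, PBMC, catecholamines, cotinine), and say whether a deferred DNA tube counts toward the daily maximum. The choice of volume is for the investigators and the assay laboratory. Any consent form that quotes a blood volume should be checked against the result.

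The cost is protocol wording and possibly a smaller tube or a stated fill volume. No visits or procedures are added.

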- When possible, a small quantity of maternal and newborn hair will be removed from the scalp as close to delivery as possible for determination of buprenorphine and metabolites.
- In the nursery, the infant will undergo standard newborn testing for signs of neonatal withdrawal (Neonatal Abstinence Syndrome, NAS). The duration and intensity of treatment will be recorded.

Maternal and umbilical cord blood and maternal and infant hair concentrations of BUP and its major metabolites will be determined by mass spectrometry. We will determine maternal cord blood concentration ratios and hair concentrations of buprenorphine and related concentrations to the severity of neonatal withdrawal symptoms.

For Specific Aim 6: Subjects who are breastfeeding and undergoing the postpartum pharmacokinetic study will also be asked to provide breast milk samples for estimation of total amount of BUP and its metabolites secreted. On this PK study day, subjects will be asked to pump the breast just prior to taking the study dose of BUP. Subjects will then take the BUP dose. Approximately every 2-4 hrs. after BUP administration, breast milk will be pumped using a breast pump and total volume measured. An aliquot of at least 1 ml but no more than 5 ml will be saved for analysis of BUP and its metabolites, and the rest of the milk will be returned to the mother for feeding the baby. In those women consenting, we will also obtain one heel stick blood sample prior to a feeding and another sample 1 hour after the feeding. Optimally, this will be done during the feeding that is as close as possible to the mother's BUP dose.

We will also perform another elective ancillary study while the baby is hospitalized or during routine postpartum PRC appointments to evaluate the time of appearance of BUP in breast milk and to assess how much drug gets into the baby's blood. We will study postpartum women who are

breast feeding and will request 1-3 samples (at least 1 ml but no more than 5 ml each) of the mother's milk for analysis of BUP. We will request 2 infant heel stick samples with each breast milk collection. One heel stick sample will be collected prior to a breast feeding (trough level) and another one 1 hour after the feeding (peak level).

D.2. Primary Research Question

The primary research questions are whether BUP and metabolite exposure (reflected as the dose-adjusted AUC) differs during pregnancy and between pregnancy and the postpartum state.

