Part D: While the baby is hospitalized, we will request 1-3 samples (at least 1 ml but no more than 5 ml each) of the mother's breast milk for analysis of BUP. We will collect 2 infant heel stick samples with each breast milk collection. One heel stick sample will be collected prior to a breast feeding (trough level) and another one 1 hour after the feeding (peak level).

Alternatively, subjects may also elect to participate in Part D during 1-3 routine postpartum PRC appointments, as long as they are still taking Buprenorphine (Subutex or Suboxone). The research staff will work with the patient to coordinate the sample collection with the timing of the patient's last BUP dose.

During each visit, we will request an infant heel stick sample prior to a breast feeding (trough level). The subject will then collect a breast milk sample. We will reserve a sample of at least 1 ml but not more than 5 ml for analysis of BUP and return the remainder to the mother for her infant. We will then collect a second infant heel stick sample 1 hour after the feeding (peak level). Ideally, we will collect both breast milk and heel stick samples during each collection; however, it is acceptable to collect only breast milk samples if the mother does not consent to the collection of heel stick samples.

Part E: We will collect 1-2 maternal blood samples while the patient is in the hospital, at least 2 days apart. We will continue to collect maternal blood samples during the subject's routine visits to the MWH BUP clinic weekly for the next 4 weeks. The time of the blood draw, the time of the last dose administration, and the dosing history will also be recorded.

D.4.i. Entry criteria include:

1. Age between 18 – 45 years
2. Currently on a stable two, three, four, or five times daily dose of sublingual BUP. Subjects participating in Part D during postpartum PRC visits must be taking Subutex or Suboxone.
3. Gestational age < 19 6/7 weeks *
4. Singleton gestation
5. Able to give informed consent and undergo study procedures
6. Willing to have urine samples screened for the presence of alcohol, barbiturates, opiates, cocaine (or metabolites), benzodiazepines, synthetic opioids and PCP *
7. Willing to participate in at least one PK study either during pregnancy or in postpartum *

*Requirement applies only to those subjects in the PK study

D.4.ii. Exclusion Criteria include:

1. Major fetal anomalies or malformations
2. HIV or AIDS

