For those women who are breast-feeding during the postpartum PK visit and wishing to participate in the breast feeding component, and if the CRC allows infants to come to the unit with their mothers, we will obtain breast milk at baseline prior to the morning BUP dose and approximately every 2-4 hours post dosing using an automated breast pump to empty the breasts. We will use at least 1 mL but not more than 5 ml of the milk for analysis of drug and metabolite concentrations and allow the mother to use the remaining milk for her infant. If these women participated in the post delivery ancillary study of breast milk, they can still participate in the postpartum PK breast milk study.

For those women consenting to the postpartum PK study, we will obtain infant blood by heel stick once prior to a feeding and again 1 hour after the feeding. Optimally this will be done during the feeding that is as close to the BUP dose as possible. In total, no baby will have more than 8 heel sticks, 6 while in the hospital or during a postpartum PRC visit as part of the postpartum ancillary study and 2 in the postpartum PK study. If the subject is not participating in the BUP PK study, the baby will have up to a maximum of 6 heel sticks (trough and peak levels on 3 occasions) as part of the postpartum ancillary study.

Upon completion of all biological fluids collection, the venous catheter will be removed and the subject will be discharged to home.

D.5.vii. Physiological Testing (Applicable to Subjects in the PK Study):

Pupillary diameter will be determined using a hand held pupillometer device (PLR-200™ Pupillometer- Neuroptics Irvine Cal.), galvanic skin response will be obtained using the Mind Ware Mobile Impedance Device, heart rate and blood pressure will be recorded by standard means. The Cravings and COW scores will be performed in conjunction with physiologic assessments at the following times:

Sample/Measurement Type	Dosing	Time Interval
physiologic	BID	Baseline and 30, 60, 90, 120, 240, 360, 480, 600, 720 minutes post dose
physiologic	TID	Baseline and 30, 60, 90, 120, 240, 300, 360, 420, 480 minutes post dose
physiologic	QID	Baseline and 30, 60, 90, 120, 240, 300, 360 minutes post dose
physiologic	5 times/day	Baseline and 30, 60, 90, 120, 180, 240, 300, minutes post dose

D.5.viii. Dietary Restrictions (Applicable to Subjects in the PK Study):

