4. The relationship between maternal dose and concentration of buprenorphine and metabolites in umbilical cord, maternal and infant hair
5. The relationship between maternal plasma and breast milk concentrations of BUP and major metabolites
6. Cumulative amount of BUP and its metabolites excreted in breast milk.

c. Secondary Outcomes Neonatal:

Neonatal outcomes to be measured include the following:

1. Relationship between concentrations of BUP and its metabolites in maternal and umbilical cord plasma and maternal and newborn hair and maternal dose and parameters of neonatal withdrawal
2. Infant hospital days
3. Birthweight
4. Gestational age
5. Neonatal Complications including: Respiratory distress syndrome (RDS), stillbirth, neonatal death, intraventricular hemorrhage as determined by cranial ultrasound, bronchopulmonary dysplasia, necrotizing enterocolitis, early onset of neonatal sepsis, seizures, retinopathy of prematurity (ROP), and hyperbilirubinemia.

D.5.xiii. Statistical Considerations

Data Analysis Plan:

The primary outcomes will be the area under the plasma concentration x time curve (AUC) of BUP during early pregnancy compared to the AUC in late pregnancy. We will also compare the AUC of BUP and metabolites during early and late pregnancy and the post-partum period. Mixed-effect models, repeated measures ANOVA or paired t-testing, will be used to compare early to late-pregnancy and overall pregnancy values to the postpartum values. Secondary outcomes such as metabolite concentrations will be analyzed in the same fashion. Additional analysis will also include multiple regressions to evaluate the relationships between maternal and fetal plasma concentrations of BUP and its metabolites, placental p-glycoprotein, physiologic parameters and CYP3A4/5 expression. We will also use population pharmacokinetic analysis to evaluate the contribution of various covariates (i.e. maternal genotype, BMI, etc.) to the observed variability in the trough plasma concentrations of BUP.

Primary Hypothesis

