We have developed a HPLC-MS-MS assay for BUP and metabolites with a lower limit of quantitation of the assay for BUP (BUP), of 0.05 ng/ml, while that for nor-BUP is 0.5 ng/ml. We have performed an intensive PK study on 12 subjects. The dose-adjusted AUC in the third trimester of pregnancy (2.4 ng/ml).hr was lower than in the postpartum period (4.0 ng/ml).hr while clearance is higher in pregnancy (589 L/hr) than in the postpartum period (288 L/hr). There was a large variation (cv = 50%) in both AUC and clearance values. None of the subjects in this cohort was studied in the first half of pregnancy.

D.7. Potential Problems, Alternative Strategies, Benchmarks

Recruitment is a potential problem in any clinical trial and if other sites in the OPPTB do not have access to patients on BUP in their own institutions they may have difficulty recruiting subjects. These patients have difficulty with compliance to drug treatment regimens so dropout may be higher than in most clinical trials. Postpartum studies are difficult because of childcare issues and this may hamper recruitment. These challenges can be overcome by identifying physicians and clinics that write prescriptions for BUP and care for such patients. The childcare issue can be addressed by financial incentives or by allowing the mother to bring her baby to the CRC during study days.

D.8. Feasibility

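### D.5.vi makes pumped milk at the postpartum PK visit conditional on the CRC admitting infants, a condition that D.1 lacks and that fits the heel sticks rather than the milk

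*Combined protocol and SAP*

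**What the plan says.** Two sections describe milk collection at the postpartum PK visit.

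- **D.1, For Specific Aim 6:** "Subjects who are breastfeeding and undergoing the postpartum pharmacokinetic study will also be asked to provide breast milk samples". A pre-dose pumping is followed by further pumping about every 2 to 4 hours, and at each of these "breast milk will be pumped using a breast pump and total volume measured". No condition refers to the CRC or to the infant being there. Heel sticks are a separate step for women who consent to them.
- **D.5.vi:** the same schedule applies to breastfeeding women who wish to take part, "and if the CRC allows infants to come to the unit with their mothers, we will obtain breast milk at baseline". The next paragraph covers infant blood without that condition: "For those women consenting to the postpartum PK study, we will obtain infant blood by heel stick once prior to a feeding".

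Three other places bear on the point.

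- **D.5.xii, maternal secondary outcomes:** outcome 5 is "The relationship between maternal plasma and breast milk concentrations of BUP and major metabolites"; outcome 6 is "Cumulative amount of BUP and its metabolites excreted in breast milk".
- **D.4, Part D:** at routine postpartum visits, "it is acceptable to collect only breast milk samples if the mother does not consent to the collection of heel stick samples".
- **D.7:** the childcare problem might be met with financial incentives or "by allowing the mother to bring her baby to the CRC during study days".

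**The concern.** The two sections give different answers to the question of who provides milk at this visit. Staff at a unit that does not admit infants would ask for milk under D.1 and not collect it under D.5.vi. The requirement in D.5.vi that the woman wishes to take part agrees with D.1, which only asks; the CRC condition alone is in conflict.

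The condition also sits on the step that does not need it. A pump obtains the milk without the infant, and neither outcome 5 nor outcome 6 uses an infant sample. A heel stick cannot be done without the infant, yet that paragraph is unconditional.

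At stake is the milk half of a paired data set. A breastfeeding woman at a unit that bars infants would complete the postpartum visit and give a full plasma profile, but no milk. Few such visits can be expected: the PK cohort is 40, only one PK study per woman is required (D.1), and D.7 expects postpartum visits to be difficult.

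**Working it through.** The plan states no target number for milk samples and no precision for outcomes 5 or 6, so there is no figure to reproduce. The check is a comparison of text, followed by a bounded count.

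**1. Which steps need the infant on the unit**

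| Step at the postpartum PK visit | Infant needed? | Condition in D.1 | Condition in D.5.vi |
|---|---|---|---|
| Pumped milk | No | Breastfeeding; woman is asked | Woman wishes to take part, and CRC admits infants |
| Heel sticks | Yes | Woman consents | Woman is in the postpartum PK study |

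In D.5.vi the admission condition is on the first row. The second row is where it would be needed.

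**2. Which data sources serve which outcome**

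| Source | Milk | Maternal plasma | Outcome 5 | Outcome 6 |
|---|---|---|---|---|
| Postpartum PK visit (D.1, D.5.vi) | Timed, total volume measured | Full profile | Yes, time-matched | Yes |
| Part D (D.4) | 1–3 aliquots of 1–5 mL; no total volume specified | None | With Part E only | No |
| Part E (D.4) | None | 1–2 samples in hospital, then weekly for 4 weeks, with dose times recorded | With Part D only, sparse | No |

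Outcome 6 needs concentration multiplied by volume, summed over the dosing interval. Only the PK visit provides that.

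**3. What one affected woman would have contributed**

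Post-dose milk samples are about the interval divided by 4 h (fewest) to the interval divided by 2 h (most), rounded down, plus one baseline sample. Intervals and plasma counts come from D.5.vi.

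| Dosing | Interval | Post-dose milk samples | Plasma samples, including baseline |
|---|---|---|---|
| BID | 12 h | 12/4 = 3 to 12/2 = 6 | 13 |
| TID | 8 h | 8/4 = 2 to 8/2 = 4 | 13 |
| QID | 6 h | 6/4, so 1, to 6/2 = 3 | 11 |
| Five times daily | 5 h | 5/4, so 1, to 5/2, so 2 | 11 |

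**4. How many women could be affected**

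The documents give no breastfeeding rate, no postpartum completion rate and no share of women seen at units that bar infants. The following are assumptions: all 40 attend the postpartum visit, 25–75% are breastfeeding, and 0–50% of those are at a unit that bars infants.

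- Lowest: 40 × 0.25 × 0 = 0 milk profiles lost; any breastfeeding rate gives 0 when no unit bars infants.
- Highest: 40 × 0.75 × 0.50 = 15 milk profiles lost, out of 40 × 0.75 = 30.

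Full attendance is generous, so with lower attendance and the same shares the loss would be below 15. A loss of precision cannot be derived from the documents, because it would depend entirely on the assumed share.

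**The case against.** The best case for leaving the text alone has five parts.

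- **The loss is hypothetical.** No section says that a CRC bars infants. D.7 raises admitting them as a remedy, and D.8 expects Pittsburgh to supply additional subjects if needed. If that unit admits infants, the effect is close to nil. This stands. A reader might infer that milk data will be lost; the documents support only that they would be lost at a unit that does not admit infants.
- **The PK visit is not the sole source for outcome 5.** This also stands. That outcome is worded without a serial profile, women may join several parts, and Parts D and E together can give milk and plasma, less closely matched in time. The claim of a sole source holds for outcome 6 and, for outcome 5, only for milk matched to a full plasma profile.
- **D.1 is an overview and D.5.vi is the operative procedure.** An overview may leave out a feasibility condition, and D.1 asks for milk rather than guaranteeing it. That makes this a drafting conflict more than two rival analysis populations. It does not explain why the condition is on the pumping and absent from the heel sticks.
- **Linking milk to infant admission may be deliberate.** Aim 6 concerns infant exposure, and the visit can last 13 hours. This is possible, but no reason is given. The fix therefore leaves the sponsor room to keep the condition and explain it.
- **Part D's allowance is not an exact precedent.** It covers a mother who declines heel sticks, not an absent infant. That is correct. It shows only that the plan regards milk without infant blood as usable.

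A reader might also infer that the remaining milk subset would be biased by site. The documents offer no mechanism linking a unit's infant policy to how the drug passes into milk, so that is not claimed here.

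**Conclusion.** The inconsistency is real and can be seen from the text alone: D.1 sets no site condition on milk, D.5.vi does, and D.5.vi leaves the heel sticks without it. The consequence is conditional. At a CRC that does not admit infants, D.5.vi as written would forgo the whole of outcome 6 for its breastfeeding women and the time-matched form of outcome 5. Whether such a unit exists is not stated. The range of 0 to 15 lost profiles is illustrative and rests on the assumptions given with it.

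The reach is limited to Aim 6 and two secondary outcomes. The primary AUC comparison and its sample size of 37 + 3 = 40 are untouched, and D.3 already accepts that some secondary questions may have too few subjects. This is a cheap improvement, not a flaw in the main analysis.

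**What to change.** In D.5.vi, take the infant-admission condition out of the milk sentence and put it in the heel-stick paragraph. Consenting breastfeeding women would then give pumped milk at the postpartum PK visit as D.1 describes, and heel sticks would be done only where the infant is present. If the sponsor has a reason to keep the condition on milk, state it and add the same condition to D.1. Either way the two sections must agree.

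The cost is one clause of protocol wording, with no new visit, sample type or blood volume. The downside is that some milk profiles will have no paired infant blood, a gap that Part D already tolerates when the mother declines heel sticks. Reports on Aim 6 should therefore give the number of women with milk and the number with milk and infant blood separately.
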